## 11 STUDY DESIGN

### 11.1 Overall Design

Up to 45 healthy subjects will participate in this study. Subjects to be enrolled in this study are indicated and scheduled to undergo optical colonoscopy based on the following symptoms or by being classified as higher than average risk based on one or more of the following:

- Surveillance - Significant findings in previous optical colonoscopy
- Diagnostic - Polyps detected in virtual colonoscopy referred for polypectomy
- Diagnostic - Polyps detected in previous optical colonoscopy (community setting) referred for polypectomy
- Diagnostic - Positive FIT test
- Diagnostic – one or more of the typical symptoms:
- abdominal pain
- Change in bowel habits
- Anemia or overt bleeding in stool
- Significant weight loss
- First degree relatives of CRC subjects

Alternatively, average risk based on their age and demographics referred for screening for polyps

Each subject will receive a comprehensive explanation regarding the study nature. During this process, and per ethical committee approval, subjects may be asked several questions (over the phone) regarding their medical background for preliminary assessment of eligibility. Once informed consent is obtained, a thorough evaluation of subject's eligibility will be performed based on inclusion / exclusion criteria. Eligible subjects will be required to undergo FIT procedure, per package insert instructions, within pre-defined timelines. All subjects will be scheduled to undergo capsule procedure, to be followed later on with optical colonoscopy procedure.

One to three days following end of C-Scan procedure the subjects will be contacted by phone by the clinical coordinator to follow-up on the subject well-being. Same follow-up procedures will be applied one to three days following Optical Colonoscopy procedure. Medical history and concomitant medication information will be collected for all subjects.

### 11.2 Study Duration

The duration of study participation for each subject is expected to be approximately 8-10 weeks. The total study duration across all patients is expected to be approximately 6 months, dependent upon subject recruitment rate.

	Document Title	Clinical Investigational Plan For Study CL-SY-02-0096		
	Document No.	DOC001593	Revision	03

## 12 SUBJECTS ELIGIBILITY

### 12.1 Study Population

The total Study population is up to 45 subjects at up to two investigational sites in the United States.

### 12.2 Inclusion Criteria

- a. Male or female at the age of 40-80 years' old.
- b. Subject provided signed informed consent.
- c. Subject is willing and able to comply with the specified study requirements and follow-up evaluations, and can be contacted by telephone.
- d. Subjects able and agrees to undergo colonoscopy procedure.
- e. BMI  $\geq 19$  and  $\leq 35$ .
- f. Maximum body (abdominal) circumference  $< 120$  cm.
- g. Has at least 3 bowel movements per week
- h. A colonoscopy procedure is pre-scheduled within 60 days

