#### 4 CLINICAL INVESTIGATION SUMMARY

Protocol Title	Evaluation of safety, usability and subject compliance while using Check- Cap's C-Scan System for providing structural information on colonic polypoid lesions and masses			
Study Number	CL-SY-02-0096			
Sponsor	Check-Cap, Inc.			
Study Design	Prospective, Multi-center, Single-arm, safety study			
Purpose	To demonstrate the safety of the Check-Cap C-Scan System			
Study Centers	Up to two (2) centers located in the United States			
Number of Participants	45 healthy subjects			
Investigational Device	Check-Cap's C-Scan System comprises C-Scan Capsule, C-Scan Track and C-Scan View.  The Check-Cap C-SCAN System is an ingestible capsule system intended to provide structural information on the endoluminal surface of the colon for the detection of colon polyps. It is intended for use in adults at average-risk for CRC who are not candidates for colonoscopy or who decline colonoscopy, or patients who had an incomplete optical colonoscopy.			
Intended use				
Primary Objective	To evaluate the safety of the Check-Cap C-Scan System.			
Secondary Objectives	
 
• To evaluate subject's compliance
 
• To evaluate subject's satisfaction
 
• To collect data to improve the product's algorithm
 
			
Primary Safety Outcome Measure	Incidence of device and procedure related Serious Adverse Events (SAE)			
Secondary Outcome Measures	
 
• Subject compliance
 
• Subject satisfaction
 
• Procedure related data for improvement of algorithm:
 
• Battery life Assessment
 
• Device performance
 
			
Inclusion Criteria	
 
1. Patients age 40 years or older
 
2. Able to provide a signed informed consent.
 
3. Willing and able to comply with the specified study requirements and follow-up evaluations, and can be contacted by telephone.
 
4. Able and agrees to undergo colonoscopy procedure.
 
5. Body Mass Index (BMI) > 19 and ≤ 35.
 
6. Maximum body (abdominal) circumference < 120 cm.
 
7. A colonoscopy procedure is pre-scheduled within 60 days
 
			

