Exclusion Criteria	
 
1. Subject who is not a suitable candidate for a colonoscopy (i.e., moderate sedation)
 
2. Known history of dysphagia or other swallowing disorders.
 
3. History of the followings: Inflammatory Bowel Disease (IBD) including Crohn's disease or Ulcerative, Colitis, Meckel's Diverticulum, Bowen Hernia, known fistulas or strictures (doctors' discretion), or a history of small bowel obstruction.
 
4. Known motility disorders: 
 
a. Chronic Constipation: less than 3 bowel movements/week, w/out the use of laxatives.
 
b. Delayed gastric emptying.
 
c. Narcotic use
 
 
 
5. Prior history of abdominal surgery that might cause bowel strictures leading to capsule retention, as determined by physician discretion with the exception of appendectomy, cholecystectomy and hysterectomy
 
6. Any condition believed to have an increased risk for capsule retention, strictures,
 
			

	Document Title	Clinical Investigational Plan For Study CL-SY-02-0096		
	Document No.	DOC001593	Revision	03

	
bowel adhesion or 'obstacles' to free passage of the capsule (such as intestinal tumors, radiation enteritis) or incomplete colonoscopies(e.g. due to obstructions or non-steroidal anti-inflammatory drugs (NSAID) enteropathy) as determined by physician discretion.
 
 
7. Has a cardiac device (e.g. pacemaker or Implantable Cardioinverter Defibrillator (ICD)) or any other implanted active device
 
8. Known sensitivity to iodine, or with known kidney failure.
 
9. Known condition which precludes compliance or is contraindicated with study and/or device instructions.
 
10. Has a Magnetic Image Resonance (MRI) procedure scheduled within 1 month
 
11. Known condition of drug abuse and/or alcoholism.
 
12. Women who are either pregnant or nursing at the time of screening (to be verified by urine or serum pregnancy test for woman of child- bearing potential who are not post-menopausal or undergone surgical sterilization.
 
13. Concurrent participation in another clinical trial using any investigational drug or device.
 

Study Duration	The total study duration across all patients is expected to be approximately 6 months, dependent upon subject recruitment rate.

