### 13.5 Visit 1: Baseline

Upon completion of the informed consent process, subject's eligibility will be assessed against the Inclusion and Exclusion criteria. Previous reports of optical or virtual colonoscopy should be collected and kept with the subject's file.

If the subject does not meet the inclusion/exclusion criteria, they will be considered a screen failure and excluded from the analysis.

The following information will be collected at this visit:

- General medical history and concomitant medication will also be assessed and documented.
- Subject's demographic and baseline information will be assessed and documented, including: date of birth, gender, height, weight, belly circumference, prior abdominal surgery, GI symptoms, and reason for referral.
- If applicable, documentation of previous GI procedures, such as optical colonoscopy

	Document Title	Clinical Investigational Plan For Study CL-SY-02-0096		
	Document No.	DOC001593	Revision	03

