### 14.1.2 Primary Analysis Set

The primary objective of the study is to establish the safety of the Check-Cap C-Scan system. The primary analysis set for establishing the safety of the Check-Cap C-Scan system will include all subjects who underwent C-Scan procedure per protocol.

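### Sections 4 and 12.2 contradict each other on who may be enrolled, chiefly on the upper age limit, and the protocol does not say whether a subject treated under one list and ineligible under the other stays in the safety analysis

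*Combined protocol and SAP*

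**What the plan says.** Inclusion criteria appear twice in the same revision of the protocol.

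- **Age.** Section 4 (Clinical Investigation Summary) has "Patients age 40 years or older". Section 12.2 has "Male or female at the age of 40-80 years' old".
- **BMI.** Section 4 has "Body Mass Index (BMI) > 19 and ≤ 35", with a strict lower bound. Section 12.2 has the same upper bound but includes the value 19.
- **Bowel movements.** Section 12.2, item g, has "Has at least 3 bowel movements per week". None of the seven inclusion items in section 4 corresponds to it. Both exclusion lists (section 4, item 4a; section 12.3, item d.i) carry the same line: "Chronic Constipation: less than 3 bowel movements/week, w/out the use of laxatives".

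The remaining inclusion items match in substance: consent, compliance and telephone contact, agreement to colonoscopy, abdominal circumference, and a colonoscopy scheduled within 60 days.

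Two places link eligibility, or conduct according to the protocol, to the analysis. Section 13.5 says: "If the subject does not meet the inclusion/exclusion criteria, they will be considered a screen failure and excluded from the analysis". Section 14.1.2 defines the primary safety set as "all subjects who underwent C-Scan procedure per protocol".

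**The concern.** Up to two sites will enrol, and each could work from a different list. The result would be a study population that does not match either stated definition, and disagreement over which subjects are protocol violations.

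The statistical consequence concerns the safety denominator. The primary outcome is the incidence of serious adverse events related to the device or the procedure, in at most 45 subjects. A subject who has swallowed the capsule has been exposed to the risk being measured. If that subject can be removed afterwards because the two lists disagree, the primary result depends on which section was consulted.

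**Working it through.** The plan gives no figure to reproduce, and section 14.1.1 states that the sample size does not come from a power calculation. The check is a side-by-side reading, followed by one piece of arithmetic.

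**Step 1: test cases, all other criteria met.**

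| Case | Section 4 | Sections 12.2 and 12.3 |
|---|---|---|
| Aged 81 | Eligible | Ineligible (12.2 a) |
| BMI exactly 19 | Ineligible | Eligible (12.2 e) |
| Fewer than 3 bowel movements a week, no laxatives | Ineligible (exclusion 4a) | Ineligible (12.2 g and 12.3 d.i) |
| Fewer than 3 a week while taking laxatives | Unclear (depends on how 4a is read) | Ineligible (12.2 g) |

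The first two rows are outright conflicts, and they run in opposite directions: section 12.2 is stricter on age and section 4 is stricter on BMI. Section 4 is therefore not simply a shortened copy of section 12.2. The third row shows no conflict. The fourth turns on whether the laxative clause describes how frequency is counted or limits the exclusion to people who take none. That ambiguity also lies inside section 12, between 12.2 g and 12.3 d.i.

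**Step 2: can a treated subject be lost?** The schedule of assessments puts the eligibility check and the capsule at Visit 1.

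1. A subject aged 81 is admitted under section 4 and swallows the capsule at that visit.
2. A later check against section 12.2 finds the subject ineligible.
3. Section 13.5 excludes from the analysis a subject who does not meet the criteria. Section 14.1.2 could be read to the same effect.
4. No section says that a subject already exposed is kept.

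**Step 3: size per subject.** The input is the maximum sample of 45 (sections 11.1, 12.1 and 14.1.1).

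- Share of the maximum sample: 1/45 = 0.022 = 2.2% for each subject.
- Illustration, assuming 45 treated subjects and a single related serious event that falls in the disputed subject: 1/45 = 2.2% if the subject is kept, 0/44 = 0% if removed.

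The documents do not say how many subjects over 80, or with a BMI of exactly 19, are expected.

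**The case against.** The strongest reply is that section 4 is headed as a summary and section 12 is the dedicated eligibility section, so a site would work from section 12. A site doing so would also satisfy section 4 on age. This reduces the practical risk. It does not remove the conflict, because no section gives one list precedence and the BMI boundary conflicts in the other direction.

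Second, the BMI difference touches a single value, and the shared constipation exclusion covers most of the bowel-movement difference. Both points stand, so age carries the finding.

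Third, section 13.5 describes screening before the capsule is given, and a subject screened out then has no capsule data to lose. The wording on the safety set in section 14.1.2 may describe only how the procedure was carried out, not who was eligible. Both readings are fair. The loss requires a subject to be treated first and reclassified later, which the protocol neither describes nor rules out.

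Fourth, keeping exposed subjects in the safety set would be sound advice even if the lists matched, so it should not add to the weight of this point. That is right. It belongs here only because it closes the route in step 2.

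A reader might also infer that subjects over 80 or with slow bowels excrete the capsule late, so that the mismatch bears directly on the primary outcome. The documents do not support this. They give no data linking age over 80 to transit time, and both lists already exclude most people with slow bowels. Delayed excretion (after 100 hours) is listed in section 16.2 as an anticipated adverse event; section 15.1.3 defines only retention beyond 300 hours as serious.

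**Conclusion.** The point holds as an internal inconsistency, not as a fault of design. The contradiction on the upper age limit is clear and is the part that matters. The BMI conflict is real but confined to a value of exactly 19. The bowel-movement difference is limited to laxative users and is partly an ambiguity within section 12.

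The effect on the analysis is a possible route, not a certain loss. It assumes that a subject is enrolled under one list, treated, and later judged under the other, and that section 13.5 or the stricter reading of section 14.1.2 is then applied. A reader might infer that the primary analysis will lose some stated share of its data. The documents give no count of affected subjects, so all that can be said is 2.2% of the maximum sample for each one. In a small descriptive pilot this still merits correction before enrolment, because a single related serious event in a disputed subject would decide whether the reported incidence is zero.

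**What to change.** Reconcile section 4 with section 12.2 so that the age, BMI and bowel-movement criteria are identical. The sponsor should decide the limits; the documents do not show which are intended. In the same edit, clarify the laxative clause so that 12.2 g and 12.3 d.i agree with each other, and with exclusion 4a in section 4.

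Add to section 14.1.2 that every subject who swallowed a capsule stays in the primary safety analysis, even if later found ineligible. Limit the screen-failure sentence in section 13.5 to subjects found ineligible before ingestion. Subjects found ineligible afterwards can be listed as protocol deviations.

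The cost is protocol wording, with the ethics approval that section 20.1 requires for an amendment. No additional subjects or data collection are needed.

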### 12.3 Exclusion Criteria

- a. Subject who is not a suitable candidate for a colonoscopy (i.e., moderate sedation)
- b. Known history of dysphagia or other swallowing disorders.
- c. History of the followings: Inflammatory Bowel Disease (IBD) including Crohn's disease or Ulcerative, Colitis, Meckel's Diverticulum, Bowen Hernia, known fistulas or strictures (doctors' discretion), or a history of small bowel obstruction.
- d. Known motility disorders:
  - i. Chronic Constipation: less than 3 bowel movements/week, w/out the use of laxatives.
  - ii. Delayed gastric emptying.
  - iii. Narcotic use
- e. Prior history of abdominal surgery that might cause bowel strictures leading to capsule retention, as determined by physician discretion with the exception of appendectomy, cholecystectomy and hysterectomy
- f. Any condition believed to have an increased risk for capsule retention, strictures, bowel adhesion or other obstacles to free passage of the capsule (such as intestinal tumors, radiation enteritis) or incomplete colonoscopies (e.g. due to obstructions or NSAID enteropathy) as determined by physician discretion.
- g. Has a cardiac device (e.g. pacemaker or ICD) or any other active implanted device
- h. Known sensitivity to iodine, or with known kidney failure.
- i. Known condition which precludes compliance or is contraindicated with study and/or device instructions.
- j. Has a Magnetic Image Resonance (MRI) procedure scheduled within 1 month
- k. Known condition of drug abuse and/or alcoholism.
- l. Women who are either pregnant or nursing at the time of screening (to be verified by urine or serum pregnancy test for woman of child- bearing potential who are not post-menopausal or undergone surgical sterilization.
- m. Concurrent participation in another clinical trial using any investigational drug or device.

	Document Title	Clinical Investigational Plan For Study CL-SY-02-0096		
	Document No.	DOC001593	Revision	03

## 12.4 Withdrawal Criteria

Subjects may withdraw from the study at their own request at any time.

The investigator may withdraw a subject from the study at any time for the following reasons:

- a. Severe side effects clearly related to the study device or procedure
- b. Less than adequate compliance with the study routine
- c. Presence or appearance of exclusion criteria
- d. Refusal to undergo 'post' colonoscopy
- e. A significant protocol violation
- f. At the specific reasonable request of the sponsor

The sponsor must be informed in each withdrawal case within 24 hours. The reason for withdrawal has to be recorded in the subject's file.

CONFIDENTIAL

The information contained in this document is confidential and the sole property of "Check-Cap"  
Any reproduction in part or whole without the written permission of "Check-Cap" is prohibited

	Document Title	Clinical Investigational Plan For Study CL-SY-02-0096		
	Document No.	DOC001593		Revision 03

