## 13 STUDY PROCEDURES AND SCHEDULE

### 13.1 Study Procedures

The C-Scan study procedures and flow are outlined in Figure 3. The schedule of study assessments are listed in Table 1. The subjects are only required to attend two visits, but are expected to conduct phone assessments after ingestion but prior to expulsion of the capsule.

*Table 1: Schedule of Assessments*

Assessments	Pre-screening	Visit 1: Baseline and C-Scan	Follow-up 1: C-Scan - During Procedure follow-up	Follow-Up 2: C-Scan Procedure End follow-up Call	Follow-up 3: Colonoscopy Post Procedure follow-up Call
Visit Window	-30-0 days	0 days	0- As required days	1-3 days post procedure	1-3 days post procedure
Questionnaire	X				
Informed Consent		X			
Inclusion/ Exclusion Criteria		X			
Demographics		X			
Medical History		X			
Concomitant Medications		X			
Pregnancy test 		X			
C-Scan procedure		X			
Connect to C-Scan		X			
C-Scan capsule		X			
Ingest contrast		X	X		
FIT test			X		
Follow up phone calls 			X		
Capsule Excretion				X	
Abdominal x-ray 				X	
Subject Satisfaction Survey				X	X
Boston Bowel Preparation Scale (BBPS)					X
Colonoscopy Report	X 				X
Follow up visit call				X	X
Adverse Events		X	X	X	
Study Exit					X

[figure not shown]
Urine pregnancy test for women of childbearing potential

Minimum of two phone calls per day until capsule excretion

Abdominal x-ray ONLY if suspected that capsule has not been excreted (subject will come to office/unscheduled visit)

Collection of a previous colonoscopy report, if available

	Document Title	Clinical Investigational Plan For Study CL-SY-02-0096		
	Document No.	DOC001593	Revision	03

	Document Title	Clinical Investigational Plan For Study CL-SY-02-0096		
	Document No.	DOC001593	Revision	03

Figure 3: Study Procedure Flow Chart

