#### 15.1.3 Capsule Retention

There is a low risk of capsule retention, *i.e.*, no excretion of the capsule after more than 300 hours (defined as SAE). Delayed capsule excretion is defined as no excretion of the capsule after 100 hours (approximately 4 days). In some instances, intervention is required to remove the capsule. Intervention, based on the physician's decision and imaging of the capsules location may include: use of laxatives, non-soluble fiber supplements, removal by colonoscopy or surgery.

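### Section 12.4 allows withdrawal with the capsule still inside but does not say whether safety follow-up continues, and the analysis-set rules may also drop the withdrawn subject from the primary safety denominator

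*Combined protocol and SAP*

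**What the plan says.** **Withdrawal (Section 12.4).** Subjects may leave at their own request at any time. In addition, "The investigator may withdraw a subject from the study at any time for the following reasons", and six grounds follow. Ground a is "Severe side effects clearly related to the study device or procedure", ground d is "Refusal to undergo 'post' colonoscopy" and ground f is "At the specific reasonable request of the sponsor". Grounds b, c and e are poor compliance, an exclusion criterion that is present or appears, and a significant protocol violation. Two duties are attached: "The sponsor must be informed in each withdrawal case within 24 hours" and "The reason for withdrawal has to be recorded in the subject's file". The section stops there.

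**General follow-up.** A footnote to the schedules in Sections 5 and 13.1 sets a "Minimum of two phone calls per day until capsule excretion". Sections 13.9 and 15.1.3 to 15.1.3.1 cover delayed passage, retention and malfunction. Sections 16.3 and 16.3.1 call for the resolution time and outcome of every adverse event. Study exit is placed only at the call after colonoscopy (Section 13.8 and both schedules).

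**Outcome and analysis.** The primary outcome is the incidence of device- or procedure-related SAEs (Section 10.3). Section 15.1.3 describes retention as "no excretion of the capsule after more than 300 hours (defined as SAE"). The primary safety set is limited to subjects whose C-Scan procedure was done per protocol (14.1.2). Capsule failures, Track failures and noncompliance are discarded from the statistical analysis (14.1.3).

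**The concern.** In a trial of a swallowed device, withdrawal does not end exposure. Section 15.1.4 says the radiation risk goes away once the capsule is excreted, so a subject withdrawn in transit stays exposed. What withdrawal may end is observation, and Section 12.4 does not say whether it does.

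The grounds are not neutral with respect to the outcome. Ground a picks out subjects with a severe related effect, who are close to the event that the trial is counting. Ground b matches a category that Section 14.1.3 discards. If contact lapses and the analysis set then excludes the same people, the primary result loses its most informative subjects from both numerator and denominator, and the bias runs towards a cleaner safety record.

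**Working it through.** There is no stated figure to reproduce: Section 14.1.1 says the sample size is not power-based. The check is mainly a comparison of sections.

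**Step 1. Does any safety provision say what happens after withdrawal?**

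| Provision | Section | Who acts, and when it ends | Mentions withdrawn subjects? |
|---|---|---|---|
| At least two calls a day | 5, 13.1 (footnote 2) | Site or trained callers, until excretion | No |
| After 100 h without known excretion | 13.9 | The subject phones; the site acts if an X-ray shows the capsule | No |
| About 4 days without excretion | 15.1.3.1 | The subject speaks to a physician; the clinic makes contact if needed | No |
| Safety malfunction | 15.1.3.1 | Clinic; removal required | No |
| Event outcome and resolution time | 16.3, 16.3.1 | Investigator | No |
| Event question at each visit or call | 16, 16.4.1 | Site; depends on there being a contact | No |
| Study exit | 13.8 | Call after colonoscopy | No |

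None of these is switched off by withdrawal, and none is said to survive it. Study exit comes at a call that a withdrawn subject may never reach. Section 13.7.1 also lets the procedure end on an audible signal, so a Follow-Up 2 call timed from the end of the procedure does not by itself show that the capsule is out.

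**Step 2. How often would an early withdrawal find the capsule inside?** Inputs from Section 8.1: total transit time with mean 52.3 h and SD 32.9 h over 63 cases. The shape is not given, so three are assumed.

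- Gamma: shape (52.3/32.9)² = 2.53, scale 32.9²/52.3 = 20.7 h.
- Lognormal: log-variance ln(1 + (32.9/52.3)²) = 0.333, log-mean ln 52.3 − 0.333/2 = 3.79.
- Normal: z = (t − 52.3)/32.9.

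| Hours after ingestion | Gamma | Lognormal | Normal |
|---|---|---|---|
| 24 | 81% | 86% | 81% |
| 48 | 47% | 44% | 55% |
| 72 | 23% | 20% | 27% |
| 100 | 9% | 8% | 7% |

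A withdrawal in the first two days would often happen with the capsule in place. At 100 h, about 3 to 4 of 45 subjects would still carry it (45 × 0.074 = 3.3; 45 × 0.088 = 4.0). Beyond 300 h these curves give at most 0.05%. They describe ordinary motility, not obstruction, so they should not be used to predict retention.

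**Step 3. Does the withdrawn subject stay in the denominator?** Section 14.1.2 does not define per protocol, so a procedure cut short under ground a could be counted or not. Ground b overlaps directly with the noncompliance discarded in 14.1.3. Section 16.1.4 lists a capsule that stays in the caecum for about 100 h or more among device malfunctions. A subject on the way to retention could therefore be classed as an operational failure and discarded too.

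**Step 4. What one lost event does, with 45 subjects.** Exact (Clopper-Pearson) two-sided 95% limits:

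- 1/45 = 2.2%. Lower limit 1 − 0.975^(1/45) = 0.06%. The upper limit solves (1 − p)^45 + 45p(1 − p)^44 = 0.025, giving 11.8%.
- 0/45: upper limit 1 − 0.025^(1/45) = 7.9%.
- If the subject also leaves the denominator, 0/44: upper limit 1 − 0.025^(1/44) = 8.0%.

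**The case against.** The strongest reply is that the safety net already exists and is tied to the capsule, not to study status. The calls run until excretion. Section 15.1.3.1 tells the clinic to make contact at about four days if needed, and requires removal after a safety malfunction. Sections 16.3 and 16.3.1 require event outcomes to be documented. SAE reporting (16.4.2) runs from the investigator's awareness and has no study-status condition. Section 8 reports more than 220 earlier ingestions with no retention and no related SAE, and this is a descriptive pilot.

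Much of that stands, and it rules out several stronger readings that a reader might draw from Section 12.4:

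- *That the protocol never requires contact until excretion, or never requires events to be followed.* The provisions just listed contradict this, although the allowed outcome codes include unchanged and unknown, so there is no duty to follow an event to resolution.
- *That a subject withdrawn at 48 h can never contribute a retention SAE.* This would need every contact to stop at withdrawal, which no section says.
- *That ground d costs safety data as a rule.* Colonoscopy follows the capsule procedure (11.1), and the schedules collect adverse events only through Follow-Up 2. Refusal after that loses no scheduled safety observation.
- *That ground f lets the sponsor remove a subject with the capsule inside after seeing the C-Scan findings.* Readings are produced after the capsule is returned (13.10). Section 8.1 also records a sponsor-initiated step after ingestion for a technical reason, depleted batteries. The documents do not support barring ground f after ingestion; listing its use is enough.

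The reply does not close the gap. The calls and visits are study procedures, and the ordinary sense of withdrawal from the study is that study procedures cease. After 100 h, Section 13.9 relies on the subject to phone. Two sites could read the text differently and both be within it. Nothing in the reply answers the denominator problem.

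**Conclusion.** The point holds as an unresolved gap between Section 12.4 and the safety sections, made worse by Sections 14.1.2 and 14.1.3. The protocol permits loss of observation after ingestion; it does not direct sites to stop.

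The change from 1/45 to 0/45 is the difference between reporting a related SAE and reporting none. It is an illustration, not an estimate. The documents give no withdrawal rate and no probability that a withdrawn subject has an unseen event, and the record in Section 8 suggests such events are rare. The illustration assumes the full 45 subjects, one related SAE in a withdrawn subject, and no contact that would reveal it. The transit percentages also rest on an assumed distribution.

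Whether data already collected may be kept after withdrawal cannot be judged here, because the consent pages were not available.

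**What to change.** - **Section 12.4:** reconcile it with Sections 5, 13.1, 13.9, 15.1.3 to 15.1.3.1, 16.3 and 16.3.1. State that after ingestion withdrawal ends optional study procedures only. Safety contacts and adverse-event collection continue, with the subject's consent, until excretion is confirmed and the Follow-Up 2 call is done. If the subject declines contact, record capsule status as unknown.
- **Sections 14.1.2 and 14.1.3:** keep every subject who ingested the capsule in the primary safety set, whatever the later withdrawal, device failure or noncompliance. Let refusal of colonoscopy affect only the agreement analysis.
- **Reporting:** list all withdrawals by ground (a to f, or own request) and by capsule status at withdrawal and at last contact.

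This concerns observation and analysis only. It proposes nothing about how a delayed capsule should be managed. The cost is protocol wording, a few extra calls per withdrawn subject and one extra listing.
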